Table 2. Roles and Responsibilities.....	19
14. Documentation Checklist.....	19
15. Reference List	19
16. Appendices.....	19

1. Study Synopsis

Study Information	
Study Type	Retrospective chart review
Study Device(s)	Profound Matrix System is a platform of 3 applicators: Sublime, Sublative RF and Matrix Pro. The Matrix Pro applicator, a new short pulse RF micro-needling device that treats with an array of RF micro-needles penetrating the skin, will be assessed in this retrospective analysis.
Indication(s)	Wrinkles
Treatment area(s)	Full face
Overall Study Objective	Evaluate the safety and efficacy of the Profound Matrix System with the Matrix Pro applicator for treatment of wrinkles
Target Enrollment	This is a retrospective chart review evaluating all subjects enrolled into the FUFT2002 source study meeting inclusion criteria and none of the exclusion criteria of this study protocol for retrospective analysis.
Study duration	N/A – this is a retrospective chart review
Study Site(s)	In the source study from which data for the current retrospective study will be extracted, subject enrollment occurred at up to five (5) clinical sites.
Study Design	This study is a retrospective analysis of de-identified subject data collected during implementation of the clinical study, “Functional Usability and Feasibility Testing of the Profound Matrix™ System (FUFT2002)” (source study). The FUFT2002 clinical study was a multi-site prospective clinical trial. The current retrospective study will analysis data extracted from the FUFT2002 database according to prespecified study selection criteria.
List of Measures	
 • Before and after photograph assessment • Subject satisfaction questionnaire • Pain/ discomfort during treatment using Numerical Rating Scale (NRS) • Adverse events evaluation
Primary Efficacy Endpoint(s)	The Primary Efficacy Endpoint is pre-defined as the percentage correct before and after photograph determinations made by blinded evaluators based on perception of facial wrinkles.

[figure not shown]
	
There will be 3 independent blinded evaluators partaking in the study. Each will receive the set of subject photographs in de-identified coded randomized order (randomized for before and after treatment presentation order with respect to each subject photograph set, and with respect to order of subject set presentation). The blinded evaluators will be required to determine within each presented photographic set which of the images is the 'Before' image (prior to treatment initiation) and which is the 'After' image (post-treatment administration) based on his or her perception of the presentation of facial wrinkles. Each blinded evaluator will perform this task independently of the other. A minimum of 2 out of the 3 blinded evaluators correctly determining Before-After assignment for an individual subject's photograph set will indicate success for that individual subject with respect to positive treatment response. 70% overall individual responder rate will be positive for study success.

Secondary Efficacy Endpoint(s)	Subject satisfaction ratings at study endpoint.
Safety Endpoint(s)	Adverse events will be tabulated by type, incidence, severity, related to treatment, action taken and outcome
Tolerability Endpoint(s)	Subject assessment of treatment discomfort/pain immediately post-treatment via Numerical Rating Scale (NRS)
Exploratory Endpoint(s)	Skin response as assessed immediately after treatment by type and severity for all subjects

2. Study Introduction and Rationale

The objective of this retrospective chart review study is to extract existing de-identified data according to prespecified study selection criteria from that collected during implementation of the clinical study, “Functional Usability and Feasibility Testing of the Profound Matrix™ System (FUFT2002)”, a multi-site prospective clinical trial. The goal of extracting this data is to evaluate the safety and efficacy of the Profound Matrix System Matrix Pro applicator for the treatment of wrinkles using pre-existing data from a clinical trial wherein the device to be evaluated for this indication was administered to study subjects per the intended treatment protocol to be administered for the treatment of wrinkles.

3. Study Device Description

Candela Corporation has developed its next generation radiofrequency (RF) system: Profound Matrix System (**Figure 1**) with Matrix Pro, Sublative RF and Sublime applicators (**Figure 2**).

Name: **Matrix Pro Retrospective Clinical Study Protocol**

Number: **MXP23001**

Effective Date: **September 21, 2023**

Revision: **01**

[figure not shown]
Name: **Matrix Pro Retrospective Clinical Study Protocol**

Number: **MXP23001**

[figure not shown]
Effective Date: **September 21, 2023**

[figure not shown]
Revision: **01**

Technical specifications for the Profound Matrix are provided in **Table 1**.

Regulatory Status

4. Investigation Plan

Study Design and Plan

A retrospective medical record (chart) review will be conducted at up to five (5) investigational sites that have prior experience treating patients with the Profound Matrix System (Candela Corporation, Marlborough, MA) for electrocoagulation and for treatment of wrinkles, acne scars or skin texture improvement. Data will be extracted from the medical records by a member of the clinical site study staff in a non-identifying manner and will include relevant demographic, safety and efficacy information but no patient identifiers. Data will be compiled and retrospectively analyzed to evaluate the treatment of wrinkles with the Matrix Pro applicator.

Study Endpoints and List of Measures

Safety will be assessed by analysis of the incidence, severity and relatedness of adverse events that were reported in the patient charts. Safety will include adverse events and optionally will include immediate skin response and discomfort during treatment.

Efficacy will be assessed by analysis of data collected by the sites from the patient chart review.

5. Study Population

Inclusion Criteria

Exclusion Criteria

1. Sun exposure during the course of the study
2. Aesthetic procedures and/or treatments during the course of the study
3. Any violation of study treatment instructions

4. Upon inspection, any differences in baseline and follow up photos that would not make evaluation of photos viable (e.g. chin placement, facial expression)
5. Any protocol deviation or change in study visit activities that would jeopardize reliability or validity of the retrospective review.

Study Participant Retention Plan

In the source FUFT2002 study, the study participant retention plan was the following: Subjects enrolled in the study can discontinue their participation at any time for any reason without prejudice or reduction in the quality of their medical care. The investigator or

Participant Compensation

As part of the FUFT2002 study, subjects received the Profound Matrix study treatment at no cost. There is no plan to compensate subjects for participation in this study.

6. Study Procedures

There are no visits for this study. FUFT2002 source study consisted of up to three treatment visits with treatment intervals 6 weeks \pm 2 weeks and follow-up visits at 1 month (4 \pm 2 weeks) and 3 month (12 \pm 4 weeks) after last treatment).

[figure not shown]
7. Ethical Conduct of the Study

This study will be conducted only after receipt of determination of exempt status by a recognized Institutional Review Board (IRB). The IRB helps protect and ensure the rights and welfare of all research participants and ensures the research is conducted in an ethical manner.

This retrospective study qualifies for 'exempt' status under human subject regulations. Exempt studies are not subject to certain federal research requirements and do not require yearly recertification.

Additionally, this retrospective study meets Health Insurance Portability and Accountability Act (HIPAA) Privacy Requirements by satisfying the criteria for waiver of privacy authorization according to the following required criteria:

All data will be collected retrospectively from existing information already recorded in the study database from subjects who were consented, qualified, and enrolled in the completed prospective clinical study, "Functional Usability and Feasibility Testing of the Profound Matrix™ System (FUFT2002)", under approval of the Allendale IRB, (IRB #00005829).

Potential Benefits and Risks

As this is a retrospective chart review there are no anticipated risks or benefits to the subjects. The risk of breach of patient confidentiality will be mitigated by use of the de-identified Patient Study Number assigned by the clinical site. The Sponsor will not request access to the clinical sites' patient charts.

8. Adverse Events

Safety management, including adverse event evaluation and reporting, is not applicable to this retrospective study as all evaluations are being performed on prior existing data.

However, as the data being evaluated under this retrospective protocol will be sourced from a prior completed prospective clinical study, safety management, including adverse event evaluation, assessment, and reporting, as applicable, was in effect under that protocol. As such, any and all adverse event information for subjects in the source study whose data is being evaluated in this retrospective study will be extracted, assessed, and reported as part of the analysis under this retrospective study protocol.

The procedures for adverse event evaluation, assessment, and reporting for all clinical studies of Candela devices and which was employed in the source study are the following:

Adverse events, and unanticipated adverse device effects (UADE) are collected from the time of subject consent until the subject exits the study. A description of the adverse event or device event, date of onset, severity, action taken, relationship to study treatment and outcome are documented in the case report form.

The Investigator submits to Candela and to the reviewing IRB/EC a report of any unanticipated adverse device effect (UADE) as soon as possible, but in no event later than 10 working days after the investigator first learns of the event (CFR 812.150(a)(1)).

[figure not shown]
Candela, upon learning of any unanticipated adverse device effect, shall immediately conduct an evaluation and report the results to FDA, all reviewing IRBs, and participating investigators within 10 working days after Candela first receives notice of the effect (CFR 812.46(b), 812.150(b)(1)).

9. Data Monitoring Plan

As this is a retrospective study, establishment of a data monitoring to ensure study and data compliance is not applicable.

The source study from which the data for analysis within this retrospective study is extracted; however, was executed under a pre-specified monitoring plan whose details were contained in the FUFT2002 source study's protocol and were in compliance with Candela Medical's Global Field Monitoring Procedure.

10. Data Management Plan

Procedures to Maintain Confidentiality

All study records and information will be identified by the subject number. All subject identifiers will be removed from all documents. Documents containing identifying information will be kept in locked files in the research staff's locked office. Limited access to electronic data will only be made available to members of the research team. No direct identifying information will be shared with any outside entities.

Protocol Deviations

All deviations will be tracked on a CRF and summarized in the progress report for the next continuing IRB/EC review.

Data Source

The data source in this study is existing information already recorded in the study database from subjects who were consented, qualified, and enrolled in the completed prospective clinical study, "Functional Usability and Feasibility Testing of the Profound Matrix™ System (FUFT2002)", under approval of the Allendale IRB, (IRB #00005829), and who satisfy the retrospective study selection criteria. This study is a pure retrospective study. No additional information will be collected for any subject in this study other than the required information that is already existing in the database from the source study.

Data Collection Methodology

For extraction of qualifying subject data from the FUFT2002 clinical study database into the current retrospective study database, the FUFT2002 data will be queried for satisfaction of the retrospective study selection criteria (inclusion/exclusion criteria). Data extraction will be strictly limited to the subject data already existing in the FUFT2002 clinical study database, and furthermore restricted to only subject entries that satisfy the retrospective study selection criteria and to only the protocol-specified data elements for the qualifying subject records.

There will be no identifying information entered into the retrospective study database that could potentially connect an individual data record to an individual subject. Unique de-identified codes will be used for each subject data set extracted from the source study database and entered into the retrospective study database.

[figure not shown]
The collected retrospective data will only be used for the purposes of evaluating the efficacy, safety, and tolerability objectives of this study.

The parties who will have access to the retrospective and source study databases will be the designated Candela employees, and the study biostatistician. Access to the database will not be given to outside parties at any time during the data collation and analysis process or in the future for any reason.

[figure not shown]
Data Elements

The following data elements will be extracted from the qualifying identified existing subject data records in the FUFT2002 study database.

1) Subject Information

2) Treatment Variables

3) Outcome Variables

e) Adverse event and other safety information

Data Storage And Management

Primary records (source study database and documents) will continue to be maintained in the respective study sites and study site subject files as before. The study data elements extracted from the source study database will be directly entered into the retrospective study database to which only the designated Candela Medical study staff and the study biostatistician will have access.

Confidentiality and Privacy

All data and records generated during this study will be kept confidential in accordance with HIPAA regulations on subject privacy. Privacy of subjects and confidentiality of the collected data elements will be secured through use of a de-identified coding system that will comprise of study subject unique study identification number. The coded de-identifiers will be used for all data entries.

Providing Results to Subjects

Results will not be provided to subjects as there is no diagnostic or otherwise medical purpose associated with this retrospective analysis that could in any potential way benefit the subjects whose data was included in the analysis or alert them to potential risks or issues in any other regard.

11. Statistical Analysis Plan

Sample Size Determination and Justification

A sample size of 24 study subjects has been determined sufficient to provide an appropriate sample population for statistical analysis and generalizability of results.

Statistical justification for sample size determination and the success criteria determination on which it is based is presented below.

[figure not shown]
Primary Efficacy Endpoint is pre-defined as the percentage correct before and after treatment photograph determinations made by blinded evaluators based on perception of facial wrinkles.

There will be 3 independent blinded evaluators partaking in the study. Each will receive the set of subject photographs in de-identified coded randomized order (randomized for before and after treatment presentation order with respect to each subject photograph set, and with respect to order of subject set presentation). The blinded evaluators will be required to determine within each presented photographic set which of the images is the 'Before' image (prior to treatment initiation) and which is the 'After' image (3-months post-treatment administration) based on his or her perception of the presentation of facial wrinkles. Each blinded evaluator will perform this task independently of the other. A

minimum of 2 out of the 3 blinded evaluators correctly determining Before-After assignment for an individual subject's photograph set will indicate success for that individual subject with respect to positive treatment response. 70% overall individual responder rate will be positive for study success.

The rationale for selection of a minimum responder rate criterion of 70% (based on a 2 out of 3 blinded evaluator concordance) is based on the minimum requirement established by the United States Food and Drug Administration (U.S. FDA) to which Candela Corporation has been upheld and successfully employed previously to attain FDA market clearance for similar devices and indications.

[figure not shown]
Employing these parameters, the minimum pre-determined sample size to provide sufficient power for a statistical comparison of the proportion of treatment responders (P) versus a reasonable cutoff (P0) is based on a power calculation utilizing the (one proportion) binomial exact test and based on the following assumptions.

[figure not shown]

Therefore, a sample size of 24 study subjects is determined to be sufficient to provide appropriate sample population for statistical analysis such that the results of this retrospective study can be considered statistically and clinically meaningful and generalizable to the broader intended population.

General Overview of Statistical Plan

Efficacy analysis will be performed for both the primary modified intent-to-treat (mITT) and the secondary per protocol (PP) populations. Safety will be evaluated for the safety population. Each is defined below.

Handling Missing Data

Missing data will be handled using the Last Observation Carried Forward data imputation method. The number and proportion of subjects with missing data will be presented in a separate table tabulated with timepoint, date, and with reasons for the missing data provided.

Tools and Resources for Data Analysis

The data will be captured by transferring specified extracted data from the source database and any other applicable study documentation directly into a database created to capture data for this retrospective study. The final database will be verified against source case report forms and locked prior to writing the final clinical study report. Data may be analyzed using Microsoft Office Excel (Microsoft, Redmond, WA) or equivalent statistical software.

The clinical findings will be consolidated and communicated using the company's Clinical Study Report Template and other deliverables as applicable (clinical bulletins, white paper, publications, etc.)

The sample size calculation and statistical analysis plan was performed by an external clinical and regulatory consultant.

12. Publication Policy

Site and Investigator shall have the right to publish the results of the trial in accordance with the clause in the clinical trial agreement, if applicable, provided sponsor has given its prior written approval. Sponsor shall have the right to review for a minimum of thirty (30) days all proposed publications or announcements related to the study and shall further have the right to require removal of information from such publication or announcement if sponsor believes removal is necessary to comply with applicable regulatory responsibilities or to allow the sponsor sufficient time to protect its intellectual property rights (IPR), through the filing of patents or the pursuit of other protection. Sponsor reserves the right to remove all Confidential Information from any publications or presentations, or if sponsor deems that such removal does not sufficiently protect its intellectual property rights, to require that investigator refrain from making such publication or

presentation. Investigator agrees that if the trial is part of a multi-center trial, any publication by investigator of the trial results shall not be made before the first multi-center publication.

13. Roles and Responsibilities

Table 2. Roles and Responsibilities

Study Personnel	Role	Responsibilities
[name]	Study Manager	Oversee study related procedures

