Sample Size Calculation and Justification	
Employing these parameters, the minimum pre-determined sample size to provide sufficient power for a statistical comparison of the proportion of treatment responders (P) versus a reasonable cutoff (P0) is based on a power calculation utilizing the (one proportion) binomial exact test and based on the following assumptions.
 

 
Therefore, a sample size of 24 study subjects is determined to be sufficient to provide appropriate sample population for statistical analysis such that the results of this retrospective study can be considered statistically and clinically meaningful and generalizable to the broader intended population.
 
 N/A, Explain rationale: N/A

Target Number of Subjects per Site	A sample size of 24 study subjects has been determined sufficient to provide an appropriate sample population for statistical analysis and generalizability of results.

GENERAL ANALYSIS CONSIDERATIONS

Timing of Analyses

- The final analysis for primary efficacy will be performed after all qualified subjects from the source study have been identified per the retrospective study inclusion and exclusion criteria and enrolled in the retrospective study, after the final data entry has been entered into the current study database, and after each of the three independent blinded evaluators have completed their Before-After blinded photographic assessments.
- The final analysis will be performed on data recorded in the electronic Excel database, having been documented as meeting the cleaning and approval requirements of SOP 10-030-01617 (Global Clinical Data Management Procedure) and after the finalization and approval of this SAP document.

Analysis Populations

Table 7

Study Design and Plan	
Full Analysis Population/ Intention to Treat Population (or Modified Intention to Treat Population):	The Full Analysis Population in this retrospective study will be the per protocol population including all enrolled subjects who had valid recorded baseline and study endpoint outcomes recorded during the source study, including evaluable photographs at both assessments. The Full Analysis Per Protocol population analysis will be the primary and only analysis population in this retrospective study.

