Adjustment of Confidence Intervals and p-values	 N/A, Explain rationale: No interim analysis is planned for this study.
Interim Analysis for Sample Size Adjustment	 N/A, Explain rationale: No interim analysis is planned for this study.
Practical Measures to Minimize Bias	 N/A, Explain rationale: No interim analysis is planned for this study.
Documentation of Interim Analyses	 N/A, Explain rationale: No interim analysis is planned for this study.

SUMMARY OF STUDY DATA

- All continuous variables will be summarized in tables using the following descriptive statistics: n, mean, standard deviation, maximum and minimum.

	Name: MXP23001 Statistical Analysis Plan	
Number: 10-040-02025	Effective Date: See Agile	Revision: A

- All categorical measures will be summarized in tables and/or charts as frequencies and/or percentages of observed levels.
- Summary tables will be structured with a column for the treatment and rows for the variables.
- Primary efficacy outcome data will additionally be listed by subject, and sorted by site, and when appropriate by visit within subject.

Subject Disposition

The following variables from the CRF will be used to establish subject disposition with respect to those selected from the source study per the current retrospective study selection criteria:

- Number received two or three study treatments and completed 1-month and 3-month follow-ups = Per Protocol population

Determination of population membership and population size per treatment group is not applicable as this study is a single arm design with no sham or control arm.

Derived Variables

The primary endpoint of blinded evaluator before/after photo determination will be derived from the photographs that are source documents recorded at the respective evaluation timepoints during the study from which the current retrospective study data will be drawn.

Protocol Deviations

There are no significant protocol deviations in the current retrospective study that could impact the study primary outcomes analysis. With respect to the source study, given that the subject selection criteria will result in a per protocol analysis population only for the current study data, there will be no major protocol deviations that could impact that study's primary outcomes analysis.

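### Exclusion criterion 4 is an open judgement on the primary-endpoint photo pairs, and the SAP has no analysis that would show the effect of those exclusions

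*Protocol*

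**What the plan says.** The primary endpoint is read from before/after photographs. A subject is a responder if at least 2 of 3 blinded evaluators order the pair correctly, and the study succeeds at a 70% responder rate (Protocol sections 1 and 11; SAP Table 2 and Primary Efficacy Analysis).

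Two exclusion criteria in Protocol section 5 call for judgement:

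- Criterion 4: "Upon inspection, any differences in baseline and follow up photos that would not make evaluation of photos viable (e.g. chin placement, facial expression".
- Criterion 5: "Any protocol deviation or change in study visit activities that would jeopardize reliability or validity of the retrospective review".

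On timing, the SAP (Timing of Analyses) places the final analysis after subjects have been identified and enrolled, after data entry, and "after each of the three independent blinded evaluators have completed their Before-After blinded photographic assessments".

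On population, SAP Table 7 requires evaluable photographs at both assessments and states: "The Full Analysis Per Protocol population analysis will be the primary and only analysis population in this retrospective study". The SAP section Secondary Analyses of Primary Efficacy Endpoint declares such an analysis not applicable, because no other population is evaluated.

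On disposition, the one item that can be read in the SAP is "Number received two or three study treatments and completed 1-month and 3-month follow-ups = Per Protocol population".

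**The concern.** Whoever applies criterion 4 looks at the outcome material and decides whether the subject counts. The criterion gives two examples of a disqualifying difference and no tolerance. Suppose the judgement that a pair is not viable is related, even unintentionally, to how much change can be seen. The retained pairs would then no longer represent the eligible subjects. Masking the evaluators and randomizing presentation order cannot undo a selection made before they read.

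With 24 subjects and a 70% rule, a few such decisions can matter. Because only the selected set is analysed, a reader of the results could not tell whether they did.

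**Working it through.** **Step 1. What controls the judgement in the visible text.**

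- *Masking.* Only the three evaluators are described as blinded. SAP Table 3 marks the study as unblinded. No role is named to apply criterion 4. Protocol section 4 has site staff extracting data, and section 10 gives database access to sponsor employees and the biostatistician. Neither group is described as masked to photo order.
- *Closing the list.* The order of steps in Timing of Analyses, and the randomizing of subject order for each evaluator, both presuppose an assembled set. Neither says that the set is then closed. The locks that are described are of the final database. In the SAP (Quality Assurance of Statistical Analysis) the lock follows entry of the evaluators' results. In Protocol section 11, "The final database will be verified against source case report forms and locked prior to writing the final clinical study report".
- *Reporting.* The Protocol's missing-data table (section 11) covers missing values, not exclusions by criterion, and the SAP calls missing-data handling not applicable. The total excluded could be derived from source-study enrolment, but not how many exclusions criterion 4 caused.
- *Another population.* Protocol section 11 says: "Efficacy analysis will be performed for both the primary modified intent-to-treat (mITT) and the secondary per protocol (PP) populations". The definitions are not visible. Criterion 4 acts at eligibility, so an mITT set of enrolled subjects would probably not restore those it removed.
- *Criterion 5* is the weaker case, because deviations leave a record: "All deviations will be tracked on a CRF and summarized in the progress report for the next continuing IRB/EC review".

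**Step 2. The plan's own figure.** N = 24 rests on an exact one-proportion binomial test with alpha 0.05 and 80% power. P0 and P are blacked out, so N can be neither confirmed nor disputed. At one-sided 0.05, an assumed P0 = 0.50 needs 17/24 (tail 0.032) and P of about 0.76 for 80% power. An assumed P0 = 0.70 needs 21/24 (tail 0.042) and P of about 0.903. I take 24 as given.

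**Step 3. Pass mark.** 0.70 × 24 = 16.8, so 17 responders (17/24 = 70.8%). The exact binomial P(X ≥ 17 of 24) is 0.0320 at p = 0.50, 0.1919 at p = 0.60 and 0.3575 at p = 0.65.

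**Step 4. Illustration of selection. Every input here except 24 and 70% is an assumption.** A fraction v of pairs is visibly improved and always read correctly. The rest are guessed. A guessed pair succeeds with probability 3 × 0.5³ + 0.5³ = 0.5, so the responder rate is p = v + 0.5(1 − v). That gives 0.60 for v = 0.2 and 0.65 for v = 0.3. Of 30 or 34 screened pairs, 24 are kept, and one type of pair is dropped at 2 or 3 times the odds of the other (200,000 simulated runs per cell).

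| True rate | No selection | Unchanged pairs dropped more often | Improved pairs dropped more often |
|---|---|---|---|
| 60% | 19% | 22-26% | 11-16% |
| 65% | 36% | 41-49% | 21-30% |

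Entries are the chance of at least 17/24. At a true 60%, the mean retained rate rises by 1.0 to 2.3 points or falls by 1.4 to 3.5. With only 3 of 27 dropped, the chance at 60% is 21% upward and 16-17% in the other direction. If all pairs are guessed, it stays at about 3.2%, because there is nothing to select on.

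If success instead required significance against an assumed P0 of 0.70 (21/24), a true 60% would pass 0.35% of the time, 0.5-0.7% with upward selection and 0.1-0.25% with the reverse.

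**Step 5. A bound that needs no selection odds.** Count k excluded subjects as non-responders. With x responders among 24, the result still passes while x/(24 + k) ≥ 0.70, that is, k ≤ x/0.70 − 24.

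| Observed | Largest k that passes | Next k fails |
|---|---|---|
| 17/24 | 0 | 17/25 = 68.0% |
| 18/24 | 1 (18/25 = 72.0%) | 18/26 = 69.2% |
| 19/24 | 3 (19/27 = 70.4%) | 19/28 = 67.9% |
| 20/24 | 4 (20/28 = 71.4%) | 20/29 = 69.0% |

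**The case against.** The best defence is that criterion 4 reduces bias. Chin position and facial expression change how wrinkles look and can give cues unrelated to treatment. The rule was written into the protocol in advance, and the SAP's sequence puts selection before the reads. That stands: the criterion should stay, and the point concerns only how it is applied and reported.

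It is also fair that much of the text is blacked out. The SAP's disposition section announces several variables and shows one, so a count by exclusion criterion may exist. A reader might infer that exclusions will go unreported, but the documents do not support that. Nor do they support the inference that subjects could be dropped once the reads are known. What is missing is a statement that the list is closed, which is not evidence that it stays open.

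A reader might also take the SAP to bar all further analysis of the primary endpoint. It does not: subgroup analyses are allowed and outcomes are listed by subject. What it rules out is another population, and neither of those allowed outputs brings back excluded subjects.

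Finally, the magnitudes are assumptions and are modest, and the 17/25 arithmetic would apply to any bare pass. Both are true. The bound shows how fragile a result would be, not that bias has occurred.

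**Conclusion.** The point holds as a change that should be made. Open judgement is applied to the endpoint photographs with no masking described. The text that says the photo-evaluable set is the only population is visible, so that part does not rest on redaction. Followed as written, the plan leaves outcome-related selection possible and its effect unmeasured.

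The direction and size of any bias are unknown. It is tempting to conclude that criterion 4 inflates the responder rate. The documents do not support that, since selection could lower the rate as easily as raise it. The shift from 19% to 22-26% or to 11-16% depends on the assumed 60% rate, two-type model, pool sizes and odds. Confidence is medium.

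**What to change.** 1. Apply criterion 4 on written pose, lighting and expression criteria, by existing staff who are not evaluators, with photo order masked and no other outcome data available. Masking the order does not by itself prevent dropping pairs that look alike. The written criteria and the log guard against that.
2. Lock a dated exclusion list with reasons, for criteria 4 and 5, before any evaluator reads. Report the number excluded by criterion in the SAP disposition table.
3. Add to the SAP a sensitivity bound that counts subjects excluded under criterion 4 as non-responders, labelled as a worst case and shown beside the main result.
4. Do not require reads of the excluded pairs. If they are done, keep them optional and exploratory, because the pose and expression cues that led to exclusion make them hard to interpret.

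The cost is protocol and SAP wording, minor relabelling of photo files, a log, and a conservative figure printed next to the main result. The main reads are unaffected. The conflict between the Protocol's mITT and PP populations and the SAP's single population is a separate matter to reconcile.
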